#### **4.1 Use of Data**

The results of the investigational study will be used for the determination of the efficacy of the intervention strategy.

The data generated during this study will support clinical trials for the prevention and monitoring of COVID-19 in HCW, FR, & DDOT bus drivers and will expand our knowledge of this disease. Any data obtained during the course of the study that may potentially significantly impact the management and/or outcomes of the proposed therapies and monitoring for COVID-10 will be made immediately available to the general health community with all related data. Barring these findings, data sharing will be planned at the completion of the study after all study plan analyses and sub-analyses have been completed.

*No personally identifiable testing for human DNA will be performed on any samples obtained from this study.*

#### **4.2 Study Duration**

Each Participant's involvement in the study will include direct contacts with study investigators which includes the following: Baseline screening, enrollment and sample acquisition; week 2-7 monitoring questionnaire, and blood samples on week 4; and week 8 study termination questionnaire and blood sample acquisition. The Participant will receive their randomized 8 week study medication supply following enrollment and randomization. The research pharmacy will

dispense medication to a dedicated study coordinator, who will then dispense the medication to the participant. All transfer of medication will be recorded on a drug accountability log for the site and in the participants' source binder. The total time for each participant in the study will be for 8 weeks from enrollment. For Participants with COVID-19 diagnosis will have an unplanned study visit after 4 weeks from diagnosis for final study assessment and blood draw. All patients may be contacted up to 30 days post completion of the study medication for safety monitoring. The study duration is estimated at 2 years for the completion of enrollment, data collection and analyses, laboratory testing to be completed, and dissemination/publication. Initial findings of the study are expected to be completed within 6 months of study initiation.

## **5 STUDY MATERIALS**

### **5.1 The following materials will be needed at enrollment (in dedicated research exam room):**

- 5.1.1** Vials of Universal Transport Media
- 5.1.2** Pre-printed labels with the site's assigned sample identification numbers for labeling the blood samples.
- 5.1.3** Blood collection kits with appropriate whole blood vials.
- 5.1.4** Cooler for sample transport to the laboratory for processing.
- 5.1.5** Study screening questionnaire
- 5.1.6** Informed consent
- 5.1.7** Thermometers
- 5.1.8** Medication Safety Sheet

### **5.2 The following materials are required for the randomization visit:**

- 5.2.1 Study medication dispensed in pill blister pack
- 5.2.2 Placebo medication dispensed in pill blister pack
- 5.2.3 Randomization form
- 5.2.4 Drug accountability log

**5.3 The following materials needed for the week monitoring visits:**

Weeks 1,2,3,5,6 & 7 will be virtual visits (via telephone, telemedicine, electronic mail as preferred by the Participant)

- 5.3.1 Questionnaire for adverse events and COVID-19 symptomatology
- 5.3.2 Call Log and Call Dialogue
- 5.3.3 Referral if symptomatic and/or the participant has a significant AE/SAE (as indicated in Pharmacy section).
- 5.3.4 AE/SAE monitoring document.
- 5.3.5 Drug accountability log

Week 4 visit will be a face-to-face visit in a dedicated research room/area.

- 5.3.6 Week 4 will require the addition of blood draw materials as in section 5.1.

**5.4 The following materials needed for the week 8 end of study visit (in dedicated research exam room):**

- 5.4.1 Questionnaire for adverse events and COVID-19

symptomatology.

**5.4.2** Referral if symptomatic and/or the participant has a significant AE/SAE (as indicated in Pharmacy section).

**5.4.3** AE/SAE monitoring document.

**5.4.4** Laboratory material as in 5.1 for sample collection and processing.

**5.4.5** Drug accountability log

## **6 STUDY SUBJECTS**

### **6.1 Number of Subjects**

Approximately 3000 HCW, FR, and DDOT bus drivers, age 18 to 75 years, without symptoms of respiratory tract infections and without a history of testing positive for SARS-CoV-2 will be prospectively enrolled and randomized at Henry Ford Health System, Detroit COVID Consortium or the Detroit Public Health Building. The fourth non-randomized comparator arm will include Participants on chronic maintenance therapy with weight-based HCQ twice a day dosing for their autoimmune disease, which will be continued throughout the study. Enrollment in this group will be open as it will be a non-randomized treatment arm, with total numbers of HCW enrolled will be expected to be lower than the randomized groups. The total study duration is expected to be up to 2 years, with Participant enrollment targeted to begin in April 2020.

Randomization Schema will be generated by the Biostatistician at Department of Public Health Sciences (PHS) at HFHS prior to the study enrollment. Randomization will be stratified by study site and level of risk of exposure in two levels. High risk includes healthcare personnel working in either hospital or nursing home settings (including environmental service) who

work in COVID-19 care areas, emergency rooms and intensive care units caring for COVID-19 patients, nursing home HCW providing any direct patient care, first responders (FR) and DDOT bus drivers. Low risk group will include healthcare and supportive personnel who work in non-COVID-19 care areas, without direct patient contact, and those involved in administrative roles. All physicians and clinical staff who are involved in the patient's enrollment and follow-ups will be blinded to the study treatments. Once enrolled, each Participant will be assigned a unique identifier. This number, along with the assigned site number, will constitute the Subject ID. This process is defined by using the following format:

□□□ - □□□□□  
Site #    Subject #

Site # = 3-digit code for the site assigned by the investigators

Subject # = 5-digit sequential number assigned by site personnel/investigators

All subject-specific material (i.e., case report log and samples) must be labeled in accordance with this ID.

## **6.2 Inclusion/Exclusion Criteria**

To be enrolled in the study, each Participant must meet all of the following inclusion criteria and none of the following exclusion criteria:

### **6.2.1 Inclusion Criteria**

1. Participant is willing and able to provide informed consent.
2. Participant is 18-75 years of age.
3. Participant does not have symptoms of respiratory infection, including cough, fevers (temperature >38.0C), difficulty breathing, shortness of breath, chest pains, malaise, myalgia, headaches, nausea or vomiting, or other symptoms associated with COVID-19.

4. Participant is willing to provide blood samples for the study.
5. Subject agrees to all aspects of the study.
6. The participant has no known allergies or contraindications (as stated in the consent form) to the use of hydroxychloroquine (HCQ) as noted in the exclusion criteria and Pharmacy sections.

### **6.2.2 Exclusion Criteria**

1. Does not meet inclusion criteria.
2. Participant unable or unwilling to provide informed consent.
3. Participant has any of the symptoms above or screens positive for possible COVID-19 disease.
4. Participant is currently enrolled in a study to evaluate an investigational drug.
5. Vulnerable populations deemed inappropriate for study by the site Principal Investigator.
6. The participant has a known allergy/hypersensitivity or has a medication or co-morbidity (including history of gastric bypass, epilepsy, cardiovascular disease or renal failure) that prevents the use of HCQ (see pharmacy section).
7. The participant is a woman of childbearing age whose pregnancy status is unknown and is not willing to use 2 methods of contraception.
8. The participant is pregnant or nursing.
9. The participant was diagnosed with retinopathy prior to study entry.
10. The participant has a diagnosis of porphyria prior to study entry.

11. The participant has renal failure with a creatinine clearance of <10 ml/min, pre-dialysis or requiring dialysis.
12. The Participant has a family history of Sudden Cardiac Death.
13. The participant is currently on diuretic therapy using loop-diuretics.
14. The participant has a history of known Prolonged QT Syndrome.
15. The participant is already taking any of the following medications: Abiraterone acetate, Agalsidase, Amodiaquine, Azithromycin, Conivaptan, Dabrafenib, Dacomitinib, Dapsone (Systemic), Digoxin, Enzalutamide, Fusidic Acid (Systemic), Idelalisib, Lanthanum, Lumefantrine, Mefloquine, Mifepristone, Mitotane, Pimozide, QT-prolonging Agents, Stiripentol). See Pharmacy section.

### **6.3 Participant Discontinuation**

Participants may discontinue their participation in the study at any time. A Participant may be withdrawn from the study at any time at the discretion of the Investigator. Participants withdrawn from the study prior to randomization will not be included in the study. Using the intention to treat (ITT) approach, participants randomized but not completing the study will be included in the study analyses based on the treatment they were assigned and worse case (test positive) will be considered for those who withdraw early and clinical COVID-19 disease status cannot be confirmed.

For this study, Participants may be discontinued from the randomized study drug if deemed to have developed a study drug related SAE. Safety follow up for up to 4 weeks after discontinuation will be done to determine clinical outcomes via direct communication with the Participant. Similarly, Participants who discontinue medications will be approached to assess any clinical outcomes during their planned 8 study week participation. Participants that are

discontinued from the study by the Investigator, are lost to follow up or decline further study involvement and withdraw their consent will not be approached after study discontinuation.

#### **6.4 Participant Withdrawal**

A Participant will be considered unevaluable for the purposes of this study if:

- Participant withdraws consent for study participation before designated baseline samples have been obtained.
- Participant refuses specimen collection at study baseline.

Subjects who are unevaluable will be withdrawn from the study and will not be included in the study analyses.

### **7 STUDY PROCEDURES**

#### **7.1 Screening and Enrollment**

Research site staff will be notified of potential Participants (i.e., Participants meeting all inclusion criteria) through screening forms filled out by potential participants on the study website, or indirect contact (in person, electronic or telephone). Research site staff will be located at different sites within participating clinical institutions to facilitate Participant enrollment (e.g., points of entry). FR and DDOT bus drivers will be informed of the study through IRB approved communications received through their work or union resources or health department flyer. All FR and DDOT bus drivers will be screened and enrolled at a participating clinical institution or health department. Research site staff trained in basic Human Research Subjects Protection will obtain informed consent from each Participant prior to enrollment and specimen collection in accordance with all applicable regulatory requirements. Those Participants wishing to participate will be asked to sign the Informed Consent Form (ICF) and will be provided with a copy for their records. The original form(s) will be maintained with the Participant's study records. Study

investigators will receive reports on eligible and enrolled study Participants on a regular basis to monitor study enrollment and accrual.

Consented Participants will be assigned a Subject ID that is recorded on the Case Report Log provided by the site investigator team. The Principal Investigator (PI) at each clinical site will maintain a Participant Master Log that will associate the Subject ID to the Subject's name and contact information. This log will remain at the clinical site and will remain confidential to the clinical site.

Clinically asymptomatic Participants not on HCQ chronic therapy will be randomized into one of the three randomized arms of the study. At that time, the research pharmacy will be notified of the subject randomization and they will prepare the 8-week supply of study medication. This will be recorded on a drug accountability log in the pharmacy. Pharmacy will notify study coordinators when medication is available for pick up and dispensing. Research coordinator will pick up the study medication and schedule a drug dispensing study visit (baseline) with the subject. At the drug dispensing study visit (baseline visit), the Participant will be given their 8-week supply of medication, which will be recorded on their individual drug accountability log. Subjects will be instructed to keep their medication blister pack and return it at the week 4 study visit and at the end of the study for a study drug reconciliation. Participants will be asked about medication adherence during their virtual monitoring visits. Participants will have a +/- 3 day window to complete their scheduled study visits. If a subject stops the study drug for any reason during the trial, the subject will be instructed to keep the remainder of their medication and return it to study personnel within 1 month for study drug reconciliation.

Asymptomatic Participants on chronic HCQ therapy will continue on their current medication for the duration of the study. If during the study period, the Participant is unable to refill their

prescription, the Study team will assess the possibility of providing the HCQ treatment for period that the Participant is unable to fill their prescription or to the end of the study (whichever occurs first).

## 7.2 Study Schedule of Events

Case Report Forms	Screening / Baseline	Randomization d	Monitoring Weeks							Study Withdrawal or Positive COVID-19 Diagnosis	Week 8 End of Study	As Needed
			1	2	3	4	5	6	7			
Pre-Screening Checklist	X											
Eligibility	X											
Baseline Survey – Pt reported	X											
Laboratory – Blood Draw	X				X					X c	X	
Randomization Form	X											
Weekly Assessment			X	X	X	X	X	X	X	X b	X	
Blinded Drug Accountability Log		X	X	X	X	X	X	X	X	X	X	
AE/SAE Log			X	X	X	X	X	X	X	X c	X	X
Concomitant medications	X		X	X	X	X	X	X	X	X	X	
Protocol Deviation Log												X
Unblinding												X
Final Status										X e	X e	

Note: a Virtual visits for monitoring will be done via telephone, video visits or electronic mail encounters, as preferred by the study participant to promote study compliance and reduce risks for participants to coming to the clinical settings and become exposed to COVID-19. b Study withdrawal evaluations due to COVID-19 infection, patient preference or other reasons may be done either by virtual visits or clinic visits, depending on the participant clinical situation. c A study questionnaire and blood draw will be attempted on each HCW/FR who test or screen positive for COVID-19 by either study or clinical screening & testing. If study testing identifies potential active SARS-COV-2 infection during the study, the investigators will notify the Participant of the results and ensure that the Participant has access to appropriate follow up care. Participants will have a +/- 3 day window to complete their scheduled study visits. d If the participant cannot receive his blister pack immediately after enrollment, the participant may return later on the date of enrollment or next day to receive their study medication. Clinical assessment will be the evaluation for symptoms during the encounter with the research personnel, any potential/ active participant describing, presenting or with clear symptoms of viral infection will be referred to their medical provider for care. e The final status form will be completed at week 8 or upon withdrawal or early termination.

### **7.3 SAMPLE COLLECTION AND HANDLING**

Five (5) 10 ml blood tubes consisting of 4 EDTA and 1 Shield tubes of whole blood will be collected from each participant at the baseline/enrollment, week 4 and week 8 timepoints. The samples will be collected using standard aseptic procedures and will be stored in a 4°C refrigerator or cooler until transport to the research laboratory where the samples will be processed. Samples will be processed to serum plasma or cell components. Testing for SARS-CoV 2 will be done for study entry samples. Remainder of the samples will be stored in -80°C for whole blood/serum plasma and cell samples will be stored in liquid nitrogen for future testing.

## **8 Statistics and Reports**

### **8.1 Case Report Form (CRF) and Questionnaires**

Study investigators will provide CRLs to sites and must include the following information:

- Participant demographics, date/time of symptoms onset, and sample collection date must be recorded.
- The study entry/enrollment (baseline visit), drug dispensing visit, week 4 and 8 visit, or at study withdrawal or confirmation of COVID-19 infection, questionnaire for each participant and submit for data entry upon completion.

If a recording error is made, cross out the error will be crossed through with one stroke, initialed and dated, with the correct information entered next to the erroneous entry.

The information required for completion of the CRL is as follows:

Subject Information:

- Subject ID (3-digit site number and 4 digit4-digit Subject number)
- Subject Gender
- Subject age

- Subject Consent Obtained (Yes/No)
- Date of Subject Consent (DD/MMM/YYYY)
- Diagnostic testing performed during the clinical visit and assay results if available
- Inclusion Criteria (Yes/No) -all criteria must be checked "yes" or Subject is not eligible
- Exclusion Criteria (Yes/No)-if any criteria is checked "yes", the Subject is not eligible
- Date of Onset of Symptom (DD/MMM/YYYY) if present
- Complete Questionnaire for each timepoint

Sample Collection Information:

- Sample Collection Date (DD/MMM/YYYY)
- Standard of Care Method/ Results
- Comments (Print Comments)

PI Signature and Date

- PI or Designee Signature and Date

## **8.2 Reporting AE and SAE – Frequency**

Completed as participant reports for SAE and in the questionnaire for mild to moderate AEs only reported during planned study timepoints.

## **8.3 Statistical Analyses and Sample Size**

The ITT will be used for testing the treatment efficacy based on patients who are SARS-CoVID-2 viremia negative at the baseline. The primary analysis will be to compare the rate of COVID-19 disease for each treatment group to the placebo group with a Mantel-Haenszel chi-square test with multiplicity adjustment using the Dunnett's step up method(11,12). The stratifying

variables will be those used for the randomization, site and High vs. Low risk groups. The high risk group include healthcare personnel (including environmental service) who work in COVID-19 care areas, emergency rooms and intensive care units caring for COVID-19 patients. First responders and DDOT bus drivers will be included as a high risk group. Low risk groups will include healthcare workers who work in non-COVID-19 care areas, without direct patient contact and those involved in administrative roles.

The DSMB chair will be provided with a weekly site SAE report to monitor safety. An interim analysis will be done when a half of patients have completed the 8 weeks assessments for an early treatment efficacy or a possible reassessment of study sample-size if the estimation of placebo rate is inadequate. Depending on response to the study intervention, the DSMB may decide it is necessary to stop/continue the trial if 1) there are safety concerns at any point in the trial or 2) there is evidence of treatment efficacy at the interim analysis; or recommendation for trial modification as it may be suggested, or 3) to continue the trial as designed. The DSMB will only stop the clinical trial for safety reasons.

Secondary analyses will be performed to evaluate the comparisons between the randomized arms and the chronic HCQ treatment comparator arm. Additional analyses will include assessments of inflammatory markers in both plasma and leukocytes, clinical characteristics associated with risk for COVID-19 acquisition, disease specific markers and clinical symptoms, as well as virologic markers and sequencing of positive COVID-19 patients during the study. Safety and AE reporting will also be done as part of the study. A detailed statistical analysis plan (SAP) will be written before the study is closed.

Sample size/power calculation:

With one planned interim analysis when 50% of the participants have completed their 8 week treatment and using an O'Brien-Fleming alpha spending method to ensure an overall type 1

error of 0.05, the critical value for the interim analysis will be 0.0054 and the final critical value will be 0.0492. With a sample size of 900 per group and  $\alpha=0.0492$ , the power to detect a 32% reduction in COVID-19 disease rate (10% vs 6.8%) between the placebo group and each HCQ treated group would be 87%. Power calculations are also given for placebo rates of 8% and 15% with a 32% reduction in COVID-19 disease rates for the HCQ treated groups. Assuming 5-10% of patients will have SARS-CoVID-2 viremia positive at the baseline, we need 1000 per group with a total of 3000 patients to complete the trial.

Power calculations using simulations for Dunnett’s step up method

Assuming 900 per group and  $\alpha=0.0492$

COVID-19 disease rate in placebo	COVID-19 disease rate in treatment	Power
8%	5.4%	80%
10%	6.8%	87%
15%	10%	98%

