Based on an $\alpha=0.05$ two-sided test, chi-square test/logistic regression with odds ratio estimates, and Haybittle-Peto alpha spending method to ensure an overall type I error, the critical value for the interim analysis will be 0.001 and the critical value for the final analysis will be 0.05. For data illustration, we have also included an O'Brien-Fleming spending function approach for controlling type I error with a critical value of 0.0054 for the interim analysis and 0.0492 for the final analysis.

Power calculations are based on $n=900$ or 935 participants per study arm, using a simulation approach ($n=10,000$ simulations) in three correction methods: #1 comparing the weekly and daily HCQ dose arms to the placebo group separately using the Dunnett's step-up approach; #2 comparing the weekly and daily HCQ dose arms to placebo separately using a conservative Bonferroni approach with critical value of 0.025 for each test at the final look; #3 comparing the combined weekly and daily HCQ dose arms to the placebo using a single test.

With Haybittle-Peto boundary and $\alpha=0.05$ at the final look, the Dunnett's step-up correction uses a closed gatekeeping strategy for testing the daily dose arm vs placebo and the weekly dose arm vs placebo separately: the largest p value tested first will be at 0.05; if that fails, the second test will be at p value 0.026, delivered from the last row of Table 2 of Dunnett and Tamhane (1992), and validated based on simulation using R *DunnettTests* package. Likewise, at the interim look, the largest p value tested first will be at 0.001; if that fails, the second test will be at 0.0005.

Table 1. Power for different scenarios using varying methods. Sample size was determined using the Dunnett's Step up method with the Haybittle-Peto boundary.

Haybittle-Peto approach	$p_0=0.1, p_1=0.073, p_2=0.063$		$p_0=0.1, p_1=p_2=0.068$	
Method	n=900	n=935	n=900	n=935
#1 Dunnett's Step up	0.800	0.811	0.770	0.800
#2 Bonferroni	0.784	0.800	0.745	0.760
#3 Daily+weekly arms vs placebo	0.812	0.83	0.819	0.835

p_0 is the rate for the placebo treated group and p_1 and p_2 are the rates for the two treated groups.

O'Brien-Fleming approach	$p_0=0.1, p_1=0.073, p_2=0.063$		$p_0=0.1, p_1=p_2=0.068$		
Method	n=910	n=935	n=900	n=935	n=970
#1 Dunnett's Step up	0.8	0.814	0.76	0.776	0.801
#2 Bonferroni	0.787	0.8	0.741	0.761	0.784
#3 Daily+weekly arms vs placebo	0.815	0.83	0.815	0.83	0.846

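### The protocol's O'Brien-Fleming thresholds 0.0054 and 0.0492 spend 0.0513, not the stated 0.05; the effect is small because the SAP adopts Haybittle-Peto

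*Protocol*

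**What the plan says.** Protocol 8.3 fixes the timing of the look: "With one planned interim analysis when 50% of the participants have completed their 8 week treatment". It attributes control of the overall type I error, at 0.05, to O'Brien-Fleming spending, and gives the thresholds as follows: "the critical value for the interim analysis will be 0.0054 and the final critical value will be 0.0492". The value 0.0492 is also the alpha used in the protocol's power table. The protocol does not mention Haybittle-Peto.

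The primary test in Protocol 8.3 is a "Mantel-Haenszel chi-square test with multiplicity adjustment using the Dunnett's step up method". SAP 6.4 states the sidedness: "two-sided test, chi-square test/logistic regression with odds ratio estimates".

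For the revised primary aim, SAP 6.4 sets Haybittle-Peto critical values of 0.001 (interim) and 0.05 (final). It adds an O'Brien-Fleming version for illustration, "with a critical value of 0.0054 for the interim analysis and 0.0492 for the final analysis". SAP 6.7 names Haybittle-Peto as the interim stopping rule.

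For the original primary aim, SAP 6.4 gives a different O'Brien-Fleming boundary for the same layout (two looks, the first at 50%, two-sided 0.05): z of 2.9626 and 1.9685, printed with p-values of 0.003 and 0.0497.

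**The concern.** Two boundaries carry the same O'Brien-Fleming label for the same number and timing of looks, yet they differ (0.0054/0.0492 against z 2.9626/1.9685). A true O'Brien-Fleming boundary trades the two looks against each other: a more generous interim level requires a stricter final level. The protocol's pair has both the more generous interim level and a slightly more generous final level (0.0492 against 0.0490, the p-value of z 1.9685). Both pairs cannot spend exactly 0.05.

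At stake is whether a printed decision threshold has the error rate claimed for it, and whether the data monitoring board would work from 0.0054 (protocol) or 0.001 (SAP) at the interim.

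**Working it through.** **Inputs.** Looks at information fractions 0.5 and 1 (Protocol 8.3); two-sided tests (SAP 6.4); nominal levels as printed.

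**Formula.** Overall alpha = 1 − P(|Z1| < c1 and |Z2| < c2), where Z1 and Z2 are standard normal with correlation √0.5 = 0.707 and c = Φ⁻¹(1 − p/2).

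**Check on the SAP's own boundary.** c1 = 2.9626 (p = 0.00305) and c2 = 1.9685 (p = 0.0490) give 0.0500, so the method reproduces the SAP's z-values. The final p-value printed beside them does not match: z 1.9685 corresponds to 0.0490, not 0.0497.

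**The protocol's pair.** p = 0.0054 gives c1 = 2.7822, and p = 0.0492 gives c2 = 1.9669. The probability of crossing at both looks is 0.0033, so overall alpha = 0.0054 + 0.0492 − 0.0033 = 0.0513 (0.05129 before rounding). The excess is 0.0013, or 0.0013/0.05 = 2.6% in relative terms.

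**Can the stated 0.05 be recovered?**

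- Rounding: the smallest values that round to the pair (0.00535/0.04915) give 0.0512; the largest (0.00545/0.04925) give 0.0514.
- Timing: 0.0520 at fraction 0.40, 0.0506 at 0.60, and 0.0500 only near 0.70.
- Both levels read as one-sided: 0.0509.
- Step-up across two arms sharing placebo: simulated family-wise error about 0.0516. This assumes second-step levels of about 0.0027 (interim) and 0.0258 (final), because the documents give none for this pair.

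**Pairs compared at 50% information, two-sided:**

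| Interim | Final | Source | Overall alpha |
|---|---|---|---|
| 0.0054 | 0.0492 | Protocol 8.3; SAP 6.4 illustration | 0.0513 |
| 0.00305 | 0.0490 | SAP 6.4 z-values, original aim | 0.0500 |
| 0.003 | 0.0497 | SAP 6.4 p-values as printed, original aim | 0.0507 |
| 0.001 | 0.05 | SAP 6.4 Haybittle-Peto | 0.0502 |
| 0.0052 | 0.0480 | classic O'Brien-Fleming | 0.0500 |
| 0.0056 | 0.0478 | Lan-DeMets spending at two-sided 0.05 | 0.0500 |

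With 0.0054 at the interim, the final level must be 0.0479. With 0.0492 at the end, the interim level can be at most 0.0026. With 0.001 at the interim, a final level of about 0.0498 gives 0.0500.

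**Power.** Take one comparison with 900 per arm and 10% against 6.8%. The drift is 0.032/√[(0.10×0.90 + 0.068×0.932)/900] = 2.45. Two-look power by normal approximation is 68.9% under 0.0054/0.0492, 68.7% under 0.00305/0.0490 and 68.9% under 0.001/0.05.

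**The case against.** The strongest reply is that the pair decides nothing. The SAP adopts Haybittle-Peto, sizes the trial on it (title of Table 1) and shows the O'Brien-Fleming pair only for illustration. Protocol 8.3 itself defers detail to a later SAP. This largely stands, and it sets the weight of the point. What remains is that the protocol prints the pair as its own thresholds, with a claim about error control that is not true of them.

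A second reply is that both documents (Protocol 8.3 and SAP 7) say the board would stop only on safety grounds. If no efficacy claim can be made at the interim, a single final test at 0.0492 stays below 0.05. That is correct as far as it goes. But the same paragraphs list interim efficacy as a ground for stopping, and SAP 6.7 says when efficacy is declared at the interim. The documents leave this open.

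A third reply is that Haybittle-Peto at 0.001/0.05 also exceeds 0.05. It does, at 0.0502, and anyone recommending it should say so. The excess is 0.0002 against 0.0013.

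A reader might infer that the trial's primary analysis runs at an inflated 0.0513. The documents do not support that, because the SAP's operative rule is a different one. A reader might also take the SAP's p-values for the original aim as a ready-made correct pair. Only the z-values hold 0.05; the printed p-values spend 0.0507.

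**Conclusion.** The statement in Protocol 8.3 is arithmetically wrong: its pair spends 0.0513 per comparison, not 0.05. This rests on two-sided tests, a look at 50% information and the usual normal approximation, and no plausible rounding or modest shift in timing removes it. The consequence is minor. It applies only if the protocol's pair is used in place of the SAP's rule and an efficacy claim is possible at the interim. The planned total of 3000 is the same in both documents and does not change. It is a correction of printed thresholds and a reconciliation of protocol with SAP, not a challenge to the SAP's primary analysis.

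**What to change.** Align Protocol 8.3 with the SAP's Haybittle-Peto rule, and state that 0.001/0.05 spends about 0.0502. If exact control is wanted, set the final level at about 0.0498. Say in both documents whether efficacy can be claimed at the interim, since the current statements conflict.

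This costs essentially no power. In SAP Table 1, step-up power with equal treatment rates is higher under Haybittle-Peto than under O'Brien-Fleming (0.770 against 0.760 at 900 per arm; 0.800 against 0.776 at 935). With unequal rates at 935 per arm it is 0.811 against 0.814. That gap is within simulation error: with 10,000 runs, the standard error is about √(0.8×0.2/10,000) = 0.004.

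If O'Brien-Fleming spending is kept in either document, replace the pair with 0.00305 and 0.0490 (z 2.9626 and 1.9685). Then rerun the figures that use 0.0492, namely the protocol's power table and the O'Brien-Fleming panel of SAP Table 1. The threshold change alone should lower power by a fraction of a point.

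In either case, correct the final p-value printed for the original aim in SAP 6.4 from 0.0497 to 0.0490. The work is a few numbers and a sentence or two in each document.
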